## **8 Measurements and procedures**

This investigation will evaluate the clinical benefit of the Virto P hearing instruments, and it will generate data to substantiate the claim that Virto P hearing instruments provide the end user with "excellent speech understanding." Virto P hearing instruments are custom, in-the-ear (ITE) devices produced by

Sonova AG under its flagship brand, Phonak. Virto P devices are intended to compensate for mild to profound hearing loss by amplifying speech and other acoustic input to a level that is audible, yet comfortable, for the patient.

One of the most important clinical benefits of any hearing instrument is to provide improved speech intelligibility in difficult listening situations. To evaluate this benefit, participants in this investigation will complete speech-in-noise testing in both an aided and unaided condition. If Virto P is providing the intended benefit, participants should, as a group, perform better in the aided condition than in the unaided condition.

For the purposes of generating data to substantiate the claim that Virto P provides “excellent speech understanding,” ‘excellent’ has been defined as the best possible speech understanding score a user is able to achieve when asked to listen to and repeat words in quiet. This maximum level of understanding will be established for each participant in the unaided condition, and testing will be repeated at a conversational level in the aided condition. Equivalence (defined as +/- 10 %-age points) between these two measures will show that users can understand as much speech as their auditory system will permit when using Virto P and listening to speech at a typical intensity level.

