## 2 Objectives

Primary objective:

- To evaluate whether adults with moderate to severe hearing loss (N3/N4) can achieve speech understanding equivalent to their individual dB-opt at a typical conversational input level while using Virto P devices in quiet.

Secondary objectives:

- To evaluate whether Virto P hearing instruments provide improved speech intelligibility in noise compared to the unaided condition in a group of adults with moderate to severe hearing loss (i.e., N3/N4).

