## **6 Endpoints**

Primary objective:

The NU-6 word lists are used extensively in the United States for clinical and research assessments of speech understanding and has been in use for over 50 years (Tillman, Carhart, Wilber, 1963). This test material was selected due to its long history of use in the United States as a measure of monosyllabic word recognition.

Performance on speech recognition tasks varies as a function of hearing loss (Guthrie and Mackersie, 2009). Not all patients will be able to reach 100% correct performance, regardless of the presentation level. Due to this variation, 'excellent' has been defined for this investigation as each individual participant's own maximum performance (PB-max). This investigation will aim to demonstrate equivalency on NU6 word recognition between aided performance at a typical level (65 dB(A)) and the participant's unaided PB-max.

Secondary objective:

The American English Matrix test was selected because it is an externally developed and validated speech test with a steep psychometric function. Because the test estimates an SNR-50, the steep psychometric function makes it a sensitive measure for comparing across multiple conditions. In this case, the test will be administered both with and without hearing aids. These results will be used to support the notion that hearing aids provide a clinical benefit (i.e., hearing speech in noise).

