## **9 Statistical design and analysis**

The sample size for this investigation was determined based on the planned analysis for the primary objective. Sample size calculation was conducted in R using the TOSTER package. The code used to generate the sample size calculation is reproduced below.

```
TOSTER::powerTOSTpaired.raw(alpha = .05,
                           statistical_power = .8,
                           sdif = 12,
                           low_eqbound = -10,
                           high_eqbound = 10)
```

The calculation above assumes an equivalence margin of +/- 10 percentage points and a standard deviation of differences of 12. The power analysis described above yielded a sample size of 13 participants at a power of 0.8 and alpha of 0.05. An additional 3 participants will be recruited to account for potential attrition and/or missing data.

Speech intelligibility data for the primary and secondary objectives from all subjects will be analyzed. A separate analysis will be conducted for the speech intelligibility in quiet measure (primary objective) and the speech intelligibility in noise measure (secondary objective). Participants will not be grouped as a part of these analyses.

The principal investigator will conduct the analysis of the primary endpoint after data has been collected from all participants for all test conditions. This analysis will be conducted in the R statistical computing environment. The analysis will follow a two one-sample t-test procedure to test for equivalency between the aided NU6 performance in quiet and the unaided PB-max performance level. In this procedure, the two one-sample tests will compare the mean difference between the two test conditions to the equivalence margin of 10 percentage points. The two tests will differ only in their alternative hypothesis; one test have an alternative hypothesis that the mean difference is greater than the equivalence margin, the other that the mean difference is less. Rejection of both tests will be interpreted to indicate that the true mean difference is within the equivalence margin above/below zero.

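### If PB-max is recorded as the highest of several unaided word scores, it overstates the true maximum, and the plan does not separate choosing the level from scoring at it

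*Combined protocol and SAP*

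**What the plan says.** Section 8 defines excellent understanding as "the best possible speech understanding score a user is able to achieve when asked to listen to and repeat words in quiet". On how that score is found it says only: "This maximum level of understanding will be established for each participant in the unaided condition". Section 6 gives the same definition under the name PB-max and notes that some patients fall short of 100% at any presentation level. Section 2 states the objective differently, as understanding "equivalent to their individual dB-opt", a term the protocol does not define.

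For the other side of the comparison, Section 8 says "testing will be repeated at a conversational level in the aided condition", and Section 6 sets that level at 65 dB(A).

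Section 9 tests the mean difference between the two conditions against 10 points in each direction. Its sample size "assumes an equivalence margin of +/- 10 percentage points and a standard deviation of differences of 12". No expected difference other than zero is entered.

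The documents do not give the number of unaided levels or lists, the words per list, whether the chosen level is retested, or how many lists are used in the aided condition.

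**The concern.** The comparator is defined as a maximum over what the participant can achieve, while the aided score is tied to one fixed level. A word-list score is a proportion with sampling error. When several such scores are taken and the highest is kept, the winner is partly the level with a favourable list, so the recorded value sits above the true plateau on average. The aided score at a fixed level receives no matching selection.

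Under that recording rule, a device that truly delivers the participant's maximum would show a negative mean difference (aided minus unaided; this sign convention is mine, as Section 9 gives no direction). Two things are at stake:

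- A failure at the lower bound could not be told apart from the scoring artefact.
- Section 9 reads rejection of both tests as placing the true mean difference inside the margin. That reading would no longer be exact, because the quantity tested would be shifted.

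**Working it through.** **Inputs from Section 9:** margin 10, SD of differences 12, alpha 0.05 for each one-sided test, power 0.8, planned n of 13, and 13 + 3 = 16 recruited.

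**Assumed, not in the documents:** binomial word scores, 25 or 50 words per list, K unaided levels, and the true score at each level.

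**1. The plan's own figure.** With an expected difference of zero, n = (z(0.95) + z(0.90))² × (12/10)² = (1.645 + 1.282)² × 1.44 = 12.33, rounded up to 13. The stated sample size therefore rests on a zero difference.

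**2. Inflation of a selected maximum, flat plateau.** For K lists of m words with the same true score p, the expected excess in points is 100 × {(1/m) Σ [1 − F(j)^K] − p}. The sum runs over j = 0 to m − 1, and F is the binomial distribution function.

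| Words | True maximum | K=1 | K=2 | K=3 | K=4 |
|---|---|---|---|---|---|
| 50 | 80% | 0 | 3.2 | 4.7 | 5.7 |
| 50 | 90% | 0 | 2.4 | 3.5 | 4.2 |
| 25 | 80% | 0 | 4.5 | 6.6 | 7.9 |
| 25 | 90% | 0 | 3.3 | 4.8 | 5.7 |

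**3. Inflation when scores vary with level.** The calculation is the same, with F(j)^K replaced by the product of the levels' distribution functions and p by the highest true score. Three levels are assumed.

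- Drops of 0/4/10 points from a best score of 70-90%: 1.2-2.4 points (50 words), 2.3-4.3 (25 words).
- Drops of 0/10/20: 0.2-0.7 (50 words), 0.9-2.0 (25 words).
- Drops of 0/20/40: 0.4 or less.
- True scores of 60/80/85% with 50 words: 1.1. True scores of 78/85/85%: 3.1.

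**4. Effect on the chance of passing.** The test passes if the mean difference minus t·s/√n exceeds −10 and the mean difference plus t·s/√n is below 10, where t is the 0.95 quantile on n − 1 degrees of freedom. Integrating over the distributions of the mean and s, with a true SD of 12:

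| Shift | n=13 | n=16 |
|---|---|---|
| 0 | 0.76 | 0.87 |
| −2 | 0.69 | 0.80 |
| −4 | 0.51 | 0.60 |

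The 0.76 at n=13 is below the planned 0.80 because step 1 is a normal approximation; that is separate from this point.

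**5. Consistency of the shift and the SD.** The shifts in step 2 come from word-sampling noise alone, whereas the SD of 12 may include other variability. Simulating the binomial model throughout, with three flat levels:

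- 50 words at 85%: shift −4.2, SD of differences 6.1, chance of passing 0.94 (n=13) or 0.97 (n=16).
- 50 words at 80%: 0.83 (n=13), about 0.9 (n=16).
- 25 words at 85%: 0.51 (n=13), 0.59 (n=16).

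**6. Upper bound.** Suppose the true aided score were 10 points above the true maximum. At SD 12 the test should then pass 5% of the time. A shift of −4 makes the apparent difference 10 − 4 = 6, and the chance of passing rises to 0.30 (n=13) or 0.35 (n=16).

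**The case against.** The strongest reply is that the protocol never describes the procedure that creates the bias. It does not say that several unaided scores are taken, that the highest is the one recorded, or that no retest follows. The dB-opt wording in Section 2 is compatible with finding a level first and then scoring at it, and a fresh score there carries no upward bias. This stands. A reader might infer that the primary endpoint has a built-in penalty of several points, or that the aided condition receives only one score. The documents support neither: they fix one aided level and do not say how many lists are given at it.

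It is also fair to say that the error would be mostly conservative. The claim in Section 8 turns mainly on the lower bound, and an inflated benchmark makes that bound harder to meet, so a pass there would be stronger evidence. This stands for the lower bound. It does not cover the upper bound, where the shift could hide a true aided excess, although an excess as large as 10 points may be unlikely.

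Finally, the power losses at SD 12 combine two sources of variation. This also stands: with 50-word lists and word-sampling noise alone, the chance of passing stays at 0.83 or above in the cases at 80% and 85%.

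The replies do not remove the gap itself. A comparator defined as a maximum, which the text links to presentation level, invites a search over levels, and the plan permits the highest score from that search to be used.

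**Conclusion.** The point holds conditionally, with moderate confidence. The direction of the bias is clear if PB-max is the highest of several scores; whether it is, and by how much, cannot be settled from the documents.

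The inflation ranges from nothing, through about 2 points where the score falls steeply away from the best level, to 2.4-5.7 points (50 words) or 3.3-7.9 points (25 words) on a flat plateau under the stated assumptions. Against a 10-point margin, even the smaller non-zero shifts matter if the SD of 12 is right. If the real SD is lower, the chance of passing at a given shift is higher than the figures at SD 12.

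The main consequence is a reduced chance of showing equivalence for a device that achieves it. The possible masking of an aided excess is secondary.

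**What to change.** In Sections 6 and 8, state the number of unaided levels, lists and words per list, and use the unaided search only to choose each participant's level. Then present one fresh unaided NU-6 list at that level, of the same length as the aided 65 dB(A) list, and name that score as the comparator in Section 9. Use one term throughout by reconciling dB-opt with PB-max: the level is what the search selects, and the score is what the fresh list gives.

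The cost is one extra list, a few minutes, for each of 16 participants, plus a few sentences of text. If the site already retests at the chosen level, only the wording changes. The downside is that a search on noisy scores will sometimes pick a slightly sub-optimal level. The fresh score then understates the true maximum a little, which makes the lower bound somewhat easier to meet and should be acknowledged in the report.

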## 4 Design of the clinical investigation

This investigation is a single-center, single-group, open-label clinical investigation. The primary aim of the present investigation is to produce evidence of the clinical benefit of Virto P devices relative to the unaided condition. Because it is unethical to knowingly deprive a group of individuals with a sensory disability (hearing loss) from a well-established treatment (hearing instruments), this trial will rely on laboratory testing in the aided and unaided conditions rather than treatment and control groups to evaluate benefit.

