## **10 Investigation Duration**

The expected duration for each participant is ~2-3 weeks.

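### NU-6 testing is worded as unaided first and aided second, with no counterbalancing or list allocation, so any practice or fatigue effect would be aliased with the aided-minus-PB-max difference

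*Combined protocol and SAP*

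**What the plan says.** - **Sequence.** Section 8 (Measurements and procedures) describes the best achievable NU-6 score as "established for each participant in the unaided condition, and testing will be repeated at a conversational level in the aided condition".
- **Contrast.** Section 6 (Endpoints) sets the aided NU-6 score at 65 dB(A) against the same participant's unaided PB-max. Section 2 (Objectives) asks whether participants "can achieve speech understanding equivalent to their individual dB-opt at a typical conversational input level". No section says how PB-max or dB-opt is obtained.
- **Design.** Section 4 says the trial will "rely on laboratory testing in the aided and unaided conditions rather than treatment and control groups to evaluate benefit", so every comparison is within participant.
- **Analysis.** The two one-sided tests in Section 9 "compare the mean difference between the two test conditions to the equivalence margin of 10 percentage points". Section 9 also states: "Participants will not be grouped as a part of these analyses". It mentions no order, period or list term.
- **Timing.** Section 10 says only this: "The expected duration for each participant is ~2-3 weeks". No section assigns tests to visits.
- **Matrix test.** Sections 8 and 9 compare aided with unaided speech in noise by a paired t-test. The order of the two runs is not stated.

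Nowhere do the documents mention counterbalancing, randomised test order, practice lists, or allocation of NU-6 lists to condition.

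**The concern.** In a within-participant comparison, test order is normally balanced so that familiarity with the task, tiredness and unequal list difficulty fall evenly on both conditions. If every participant is tested unaided and then aided, the observed mean difference estimates the true aided-minus-PB-max difference plus the order effect. The data cannot separate the two parts, and more participants do not help.

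The primary result is meant to support a claim of excellent speech understanding, so the error that matters most is declaring equivalence when aided performance is materially worse. A practice gain on the second test pushes towards that error. Fatigue pushes away from it, but can make a device that truly matches PB-max fail. If the Matrix runs were also done unaided first, a practice gain there would count as hearing-aid benefit.

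**Working it through.** **Inputs from Section 9:** margin 10 percentage points, SD of paired differences 12, alpha 0.05 for each one-sided test, power 0.8, stated n = 13, plus 3 for attrition = 16. **Assumed, not in the documents:** an order shift δ of 1, 2 or 3 points on the second test, with aided tested second.

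**1. The plan's own figure.** Normal approximation, true difference 0:

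n = (z₀.₉₅ + z₀.₉₀)² × (SD/margin)² = (1.645 + 1.282)² × (12/10)² = 8.564 × 1.44 = 12.33, rounded up to 13. The stated sample size reproduces and is not affected by this point.

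**2. Effect of one fixed order.** With true difference θ, the mean paired difference is distributed as N(θ + δ, 12²/n). Equivalence is declared when |mean| < 10 − t₀.₉₅,ₙ₋₁ × s/√n. The probability is obtained by integrating over the distribution of s².

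- n = 13: SE = 12/√13 = 3.328, t = 1.782.
- n = 16: SE = 12/√16 = 3.000, t = 1.753.

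| Shift δ (points) | False equivalence at θ = −10, n = 13 | Same, n = 16 | Power at θ = 0, n = 13 | Same, n = 16 |
|---|---|---|---|---|
| 0 | 5.0% | 5.0% | 0.764 | 0.875 |
| +1 | 8.7% | 9.2% | 0.745 | 0.856 |
| +2 | 14.0% | 15.7% | 0.692 | 0.800 |
| +3 | 21.3% | 24.5% | 0.611 | 0.713 |

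Power is symmetric in δ, so fatigue of the same size gives the same power. Fatigue of 2 or 3 points lowers false equivalence to 1.3% or 0.6% (n = 13) and to 1.1% or 0.5% (n = 16). The false-equivalence error caused by practice is larger at n = 16 than at n = 13, because a bias weighs more as the standard error shrinks.

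**3. Balanced order with an order term.** The estimate is the average of the two order-group mean differences, with pooled variance, n − 2 degrees of freedom and SE = 12 × √(1/n₁ + 1/n₂)/2.

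| Split | SE | Power at θ = 0 | False equivalence at θ = −10 |
|---|---|---|---|
| 8/8 | 3.000 | 0.872 | 5.0% |
| 7/6 | 3.338 | 0.754 | 5.0% |
| 8/5 | 3.421 | 0.725 | 5.0% |

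The 5.0% assumes that the order effect is the same size in both orders.

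**4. Balanced order without an order term.** By simulation with a 3-point practice gain, an 8/8 split gives false equivalence just under 5% and power of about 0.86. An 8/5 split gives false equivalence of about 6.7% if the larger group is tested aided second, and power of about 0.73. Balancing therefore does most of the work, and the term matters mainly when dropout unbalances the groups.

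**The case against.** The strongest reply is that the Section 8 sentence explains how excellent performance is defined and is not a visit schedule. That stands. A reader might infer that the plan mandates unaided-first testing for everyone, but the documents only imply it. If the order is instead left to the tester, it is uncontrolled, and the aliasing figures above do not apply as they stand.

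Second, nothing in the documents shows that an order effect exists, how large it is or which way it acts. That also stands. At 1 point the consequences are modest, and the false-equivalence figures require a true deficit exactly on the margin. However, data collected in a single sequence could never reveal the effect.

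Third, a reader might take the sentence about not grouping participants, or the absence of a control group, as ruling out an order term. Neither does. The sentence can simply mean no subgroups such as N3 and N4, and a within-participant comparison needs no control group to balance order. The order term is merely absent.

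Fourth, the devices are custom-made. If PB-max is scored before the device is available, aided-first testing needs another unaided list later. This is fair and is counted as a cost of the fix.

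**Conclusion.** The point holds conditionally. If the Section 8 wording is followed, any practice or fatigue effect is fully aliased with the difference that the primary test examines. An assumed practice gain of 1 to 3 points raises false equivalence from 5% to between 8.7% and 21.3% (n = 13) or between 9.2% and 24.5% (n = 16). A shift of that size in either direction lowers power to between 0.745 and 0.611, or between 0.856 and 0.713. These figures rest on the plan's SD of 12 and on assumed shifts. With no order effect there is no bias.

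The documents do not support the reading that the result will be biased. Nor do they support the inference that PB-max overstates true performance because it is the highest of several scores: neither the scoring method nor the list length is stated, and a single list at a chosen level would carry no such selection effect.

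This is a worthwhile, inexpensive improvement to how the primary endpoint is collected. It is not a flaw that invalidates the design.

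**What to change.** **Section 8.** After the device is fitted, score the unaided best-level and aided 65 dB(A) NU-6 conditions in counterbalanced order, 8 participants in each order for the 16 recruited, with different word lists randomly assigned to condition. An earlier unaided level search may remain if it serves only to choose the level. This is feasible because the aided level is fixed and does not depend on the PB-max result. Counterbalance the aided and unaided Matrix runs in the same way.

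**Section 9, optional.** Add order as a term in the equivalence test (n − 2 degrees of freedom) to protect against unequal groups after dropout. If it is added, clarify that the sentence on grouping does not exclude it.

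**Cost.** An order schedule, and one further unaided list at the fitted-device visit if PB-max would otherwise be scored before the custom device is available. If the term is adopted, power with an even split at n = 16 goes from 0.875 to 0.872. At n = 13 it goes from 0.764 to 0.754 (7/6), or to 0.725 if all three losses fall in one order (8/5).

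### Does the plan leave open what it means for the excellent-speech-understanding claim if only the upper equivalence bound is missed?

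*Combined protocol and SAP*

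**What the plan says.** Four sections of the combined protocol and SAP bear on this point, and all four ask for equivalence.

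- Section 2 sets the primary objective as "speech understanding equivalent to their individual dB-opt at a typical conversational input level". It calls the comparator dB-opt where Sections 6 and 9 say PB-max; that difference in terms does not affect this point.
- Section 6 says the investigation will "aim to demonstrate equivalency on NU6 word recognition between aided performance at a typical level" (65 dB(A)) and the unaided PB-max.
- Section 8 defines excellent as "the best possible speech understanding score a user is able to achieve" and gives the condition for the claim: "Equivalence (defined as +/- 10 %-age points) between these two measures will show that users can understand as much speech" as the auditory system allows.
- Section 9 names the test: "The analysis will follow a two one-sample t-test procedure to test for equivalency between the aided NU6 performance in quiet and the unaided PB-max performance". It gives the decision rule: "Rejection of both tests will be interpreted to indicate that the true mean difference is within the equivalence margin above/below zero". The sample size code sets the bounds at -10 and +10 with an SD of differences of 12, and the calculation "yielded a sample size of 13 participants at a power of 0.8 and alpha of 0.05". Three more participants are recruited for attrition, making 16.

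No section states in so many words what follows if only one of the two tests rejects.

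**The concern.** If PB-max really is the most a listener can score, an aided score can contradict the claim only by falling short of it. The conclusion in Section 8 therefore sounds one-directional, while the test in Section 9 has two bounds. Taking the difference as aided minus PB-max, the two ways to fail look different. Missing the lower bound leaves a shortfall of 10 points or more possible. Missing only the upper bound excludes such a shortfall, and yet the trial fails.

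Because only joint rejection is interpreted, it is natural to ask whether the sponsor could decide after seeing the data that an upper-only miss still supports the claim. The trial is open-label and the principal investigator runs the primary analysis. If that choice were truly open, either the claim would be lost in trials with no material shortfall, or it would be rescued by dropping a bound after the fact.

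**Working it through.** **Step 1: the rule in the text.** Section 8 has the form: if equivalence within 10 points, then the conclusion. Section 9 supplies the test of the condition: both one-sided tests reject.

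| Lower test | Upper test | Equivalence (Section 9) | Section 8 conclusion |
|---|---|---|---|
| rejects | rejects | shown | drawn |
| rejects | does not | not shown | not drawn |
| does not | rejects | not shown | not drawn |
| does not | does not | not shown | not drawn |

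Every outcome has a reading. For an upper-only miss to carry the claim, the plan would have to say that absence of a shortfall is enough, and no section says this.

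**Step 2: does the conclusion follow when the trial succeeds?** Joint rejection includes rejection at -10. If the true mean shortfall is 10 points or more, the lower test rejects with probability at most 0.05, and requiring the upper test as well can only lower that. The two-sided test is thus at least as strict as a one-directional claim needs.

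**Step 3: the plan's own figure.** Inputs from Section 9: alpha 0.05 per test, power 0.8, SD 12, margin 10. The true difference is not stated; 0 is assumed. With the normal approximation,

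n = (z₀.₉₅ + z₀.₉₀)² × 12² / 10² = (1.645 + 1.282)² × 1.44 = 12.33, rounded up to 13.

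This matches the stated 13, which supports the assumption of 0.

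**Step 4: how often only the upper bound is missed.** The upper test fails when the observed mean exceeds 10 - t(0.95, n-1) × SD/√n. With an observed SD of 12:

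- n = 13: 10 - 1.782 × 12/√13 = +4.1
- n = 16: 10 - 1.753 × 12/√16 = +4.7

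The table integrates the t-based tests over the sampling distribution of the variance, with a true SD of 12. Simulation of 1,000,000 trials at a true difference of 0 agrees with it.

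| True difference | Both reject, n = 13 / 16 | Upper-only miss, n = 13 / 16 | Share of failures, n = 13 / 16 |
|---|---|---|---|
| 0 | 0.764 / 0.875 | 0.118 / 0.063 | 50% / 50% |
| -1 | 0.745 / 0.856 | 0.071 / 0.032 | 28% / 22% |
| -2 | 0.692 / 0.800 | 0.040 / 0.015 | 13% / 8% |
| -3 | 0.611 / 0.713 | 0.021 / 0.007 | 5.5% / 2.3% |

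The share at 0 is 0.118 / (1 - 0.764) = 0.50 for n = 13 and 0.063 / (1 - 0.875) = 0.50 for n = 16. It is one half because the bounds are symmetric about the assumed truth and missing both bounds is almost impossible (0.006% at n = 13). Any test of this kind gives the same split. If PB-max is a true maximum, the true difference is at most 0, so one half is the largest share to expect.

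(The t-based power of 0.764 at n = 13 is below the nominal 0.8 because Step 3 uses the normal approximation, which gives 0.826. This does not bear on the present point.)

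**Step 5: what the upper bound costs.** If the lower test alone decided, the chance of success at a true difference of 0 would be 0.882 (n = 13) or 0.937 (n = 16). The upper bound therefore costs 0.882 - 0.764 = 0.118 or 0.937 - 0.875 = 0.063 in power. It adds no false claims.

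**The case for a change.** The best argument for the concern is that the sponsor has two targets, the equivalence objective and the claim of excellent speech understanding. An upper-only miss fails the first, but a sponsor might say that it meets the second. The outcome would also carry information: if aided scores materially exceed a supposed maximum, PB-max may have been measured too low, which makes the lower test easier to pass. The documents give no presentation levels or search procedure for PB-max. Suppose, as an assumption outside the documents, that PB-max is under-measured by 13 points and the true shortfall is 10, so the measured difference is +3. The two-bound test then passes with probability 0.611 (n = 13) or 0.713 (n = 16), against 0.979 or 0.994 on the lower test alone.

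Part of this stands. The plan has no explicit sentence on one-sided rejection, and one would do no harm.

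The rest does not. Section 8 makes the claim depend on equivalence, so the two targets share one decision rule. The figures of 0.979 and 0.994 arise only if the sponsor abandons that rule, which would be a departure from the plan and not a gap in it. The same scenario shows that the upper bound is a weak check on PB-max, since the test still passes in 61% or 71% of such trials. No section gives the bound that purpose. At a true difference of 0, upper-only misses are sampling error, and reading them as evidence against PB-max would mislead.

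**Conclusion.** The concern does not hold. An upper-only miss means that equivalence is not shown, so the Section 8 conclusion is not drawn. When both tests reject, that conclusion is supported to within the stated 10 points. The probability of an upper-only miss is 11.8% with 13 participants and 6.3% with the planned 16, at a true difference of 0 and an SD of 12. It falls to 2.1% and 0.7% at a true difference of -3. These figures measure the power spent on a two-sided objective and do not point to an invalid inference.

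This rests on three readings: the bounds are -10 and +10, as in the sample size code; the difference is aided minus PB-max, an order the documents do not fix; and the planned true difference is 0, which is implied but not stated. The reading of the decision rule depends only on the first. A sentence spelling out the one-sided outcomes would record what the text already implies and would change no test, margin, sample size or decision.
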